#### 14.4 Data Integrity:

Despite efforts, it is possible that some data will be missing, which could limit the interpretation and generalizability of results. If the data are missing at random, conditioned on measured covariates, then supplementary analyses adjusting for these covariates will produce unbiased results. For potential missing data mechanisms beyond measured covariates, we will examine the extent to which results may be affected. Imputation techniques will be considered for missing data issues (e.g., multiple imputation). In particular, for the primary analysis we will use a last observation carried forward approach for participants on whom we do not have a final measurement. Additional complementary analyses will incorporate Markov Chain Monte Carlo (MCMC) multiple imputation to handle missing data. The imputation model will be stratified by treatment group and include baseline values at randomization. Additional variables for possible inclusion in the model include age, race, sex, and Tanner stage, though unlikely to be more than one in any single model due to sample size limitations. MCMC imputation will be used to estimate treatment group differences, 95% confidence intervals and P values; observed data will be used to estimate within treatment group changes. If the analyses with and without multiple imputed values differ

substantially, then exploratory analyses will be performed to evaluate factors that may have contributed to the differences. Secondary endpoints will be handled similarly.

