Week 24 and Week 52: Participants will present for an in-person visit for a physical examination. Tanner staging, height and weight measurements will be collected. Vital signs (BP and HR) will also be collected. Contraceptive counseling and lifestyle management will again be given. Participants will be asked about adverse events that they have experienced. Blood will be drawn for a hemoglobin A1c, basic metabolic panel, lipid profile, and a Vitamin D 25. A review of the participants' daily insulin doses will be reviewed. Any co-administered medications will be discussed. Participants will have the OGTT testing and blood will be collected at the outlined timepoints for plasma glucose levels, c-peptide levels and insulin levels. Approximately two tablespoons of blood will be drawn at the visit. Participants will be asked to complete the EDE-Q, PedsQL, PHQ-9 and C-SSRS evaluations. Urine pregnancy test will be done and reviewed if applicable. An iDXA for total body fat, visceral fat and bone mineral density will be conducted. The participant will have their CGM data reviewed and new CGM sensors will be provided at week 24. The participant's insulin dose will be reviewed and their adherence to the study medication will be assessed. Study medication will be distributed for week 24. Instructions on how to down-titrate off the study medication will be done on week 52. Participants who elect to upload their CGM data remotely before the visit may elect to receive study medication, home urine pregnancy tests, and sensors to last them for the remainder of the study.

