### *11.3 Termination Procedures:*

Participants who withdraw from the study will not have additional study information collected. Data that had been collected prior to their withdraw will still be reviewed and utilized.

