### 14.3 Statistical Analysis:

Descriptive analyses of baseline characteristics and outcomes will include means and standard deviations, median and range for continuous variables and frequencies for categorical variables. Treatment adherence will also be evaluated by the methods described above. Safety analyses will be primarily descriptive reporting the number and percentage of adverse events. All safety outcomes will be evaluated and monitored throughout the trial. Confidence intervals (CIs) and p-values will be based on robust variance estimation. Statistical significance will be considered as  $p < 0.05$ .

Aim 1: The primary analysis will be conducted using the ITT population to compare the mean BMI percent change (primary outcome measure) from randomization to 6 months of follow-up between the groups, adjusted for BMI at randomization for added precision. We hypothesize that with participants treated with PHN/TPM will demonstrate greater BMI percent change compared to controls at 6 months. Supportive analyses using the PP population will also be conducted along with consideration of adjustment for residual imbalances

between treatment groups after randomization (e.g., in sex as a biological variable). Longitudinal analyses will also be conducted, incorporating the multiple time points through the open-label extension (6 months to 12 months follow-up) during which these BMI measurements will be obtained. This will examine durability of changes observed over the masked portion of follow-up, as well as provide additional safety information. Supportive analyses using the PP population will also be conducted.

Aim 2: Secondary outcomes will be analyzed in the same fashion as the primary endpoint wherein analyses will be adjusted for values at randomization. Outcome measures for Aim 2 are c-peptide index ( $\Delta C_{30}/\Delta G_{30}$ ), insulin sensitivity (1/fasting insulin),  $\beta$ -cell function relative to insulin sensitivity (oral disposition index [oDI]), A1c (%), and total daily insulin dose (units/kg/day). We hypothesize that participants treated with PHN/TPM will demonstrate improved insulin sensitivity and  $\beta$ -cell function compared to those assigned to placebo as measured by OGTT, A1c and total daily insulin doses. Complementary secondary analyses will also be conducted for each secondary outcome as described for the primary outcome.

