**Participant Safety:** At the outset, participant risk will be minimized by study team adherence to exclusion and inclusion criteria during screening. The proposed research will expose the participants to a minor increase over minimal risk. The exclusion criteria include, but are not limited to, contraindications to PHN/TPM. Participant assessments will be done at study visits every three months. Participants and their parent/guardian (if < 18 years) will be provided with contact information for [name] (study PI), clinical nurse, and the research coordinator with explicit instructions to contact the study team in the event of emergencies.

**Participant Stopping Rules:** In the event that a participant has a serious adverse event that is deemed related to the study medication and/or procedures by the PI, the participant will be required to immediately discontinue the intervention. The overall study may be stopped at any time at the request of the PI and/or the DSMB. Participants will be removed from the study if suicidal ideation, excessive

weight loss, or disordered eating is present at any time during the trial or if any clinically significant changes (at the discretion of the PI) in mood and/or depression are observed. If the ratio of participants on medication vs. placebo developing a serious adverse event requiring withdrawal exceeds 4:1 (after  $\geq 50\%$  enrollment and a minimum of 5 total events, regardless of group assignment), the trial will be stopped. Patients will be instructed that they may withdraw from the study at any time and for any reason without impact on their typical clinical care.

**Study Integrity:** As stated above, the study will undergo annual monitoring of the facility, staff, and study documents by clinical research associates of the University of Minnesota Clinical Trials Monitoring Service. Monitoring staff will provide a summary report to [name] and her mentorship team after each site visit. If necessary, corrective action plans will be devised and implemented by [name] to address deficiencies.

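### Last observation carried forward as the primary missing-data rule enters a missing week-24 OGTT as exactly zero change; for BMI it adds a small bias at 10% attrition whose size and sign depend on which arm loses participants

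*Combined protocol and SAP*

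**What the plan says.** Section 14.3 makes the primary analysis an intention-to-treat comparison of percent change in BMI from randomization to 6 months, adjusted for baseline BMI. Aim 2 is analysed in the same way.

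For missing data, section 14.4 states that "for the primary analysis we will use a last observation carried forward approach for participants on whom we do not have a final measurement". Multiple imputation has a supporting role: "Additional complementary analyses will incorporate Markov Chain Monte Carlo (MCMC) multiple imputation to handle missing data". That imputation is by treatment group from baseline values. Age, race, sex or Tanner stage may be added, but "unlikely to be more than one in any single model due to sample size limitations". Interim weights are not listed. The section closes with "Secondary endpoints will be handled similarly".

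The measurement schedule (section 5.1 Schedule of Events, sections 5.2 and 8.3) is:

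- OGTT at baseline, week 24 and week 52 only. Section 8.3, under Week 24 and Week 52, says "Participants will have the OGTT testing and blood will be collected at the outlined timepoints". Under section 5.2, an attendee who has not withheld insulin skips the test and is asked back within a week.
- Height and weight at weeks 0, 12 and 24; weight alone at weeks 4, 8, 16 and 20.

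On leaving the trial, section 11.3 says "Participants who withdraw from the study will not have additional study information collected". Section 11.2 offers the option of stopping drug but continuing visits. Section 17.2 removes participants for, among other reasons, excessive "weight loss, or disordered eating is present at any time during the trial".

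**The concern.** LOCF answers the 6-month question with a value from another time. For the OGTT outcomes that value can only be baseline, so a missing result is analysed as a participant whose insulin sensitivity and beta-cell function did not change. This does not require dropout: someone who attends week 24 without having withheld insulin and does not return is handled in the same way.

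For BMI the carried value comes from weeks 0 to 20. Under section 4.1 the top dose is reached only after three 14-day steps (6 weeks), so a value carried from week 0 or 4 precedes it.

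Missingness need not be random or balanced. Section 17.2 contains a removal rule tied to weight loss, withdrawal ends data collection, and section 14.2 gives 10% attrition with no split by arm. At stake is a bias that is built into the primary estimate and that supporting analyses do not remove from it.

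**Working it through.** **The plan's own figures (section 14.2).** Baseline-adjusted SD = 8.9 × √(1 − 0.75²) = 5.89. Detectable difference = (1.96 + 0.84) × 5.89 × √(2/n): 6.02 at n = 15 per arm and 6.35 at n = 13.5, against the stated 6% and 6.3%. These reproduce (two-sided 0.05 assumed). The standard error at n = 15 is 5.89 × √(2/15) = 2.15.

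**OGTT outcomes.** With missing shares dA and dP and true mean changes μA and μP, the zero-change rule gives (1 − dA)μA − (1 − dP)μP. The arm changes below are assumed, in arbitrary units.

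| 3 of 30 missing | μA, μP | True difference | Rule gives |
|---|---|---|---|
| 10% in each arm | any | D | 0.9D (−10%) |
| All 3 active (dA = 0.2) | 10, 0 | 10 | 8.0 (−20%) |
| All 3 active | 0, −10 | 10 | 10.0 (0%) |
| All 3 active | −2, −10 | 8 | 8.4 (+5%) |
| All 3 placebo (dP = 0.2) | 15, 5 | 10 | 11.0 (+10%) |

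A1c and total daily insulin dose have week-12 values, so they are not forced to zero in the same way.

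**BMI.** Shrinkage of the difference = dA·RA − dP·RP, where R is the mean loss still to come in that arm after the last observation. Assumptions: true difference 6 points, placebo flat (RP = 0), last visit spread evenly over weeks 0, 4, …, 20. For a linear course with monthly weights, R = (6+5+4+3+2+1)/6 = 3.5. If only visits with measured height count, R = (6+6+6+3+3+3)/6 = 4.5. The exponential course is 6(1 − e^(−w/10))/(1 − e^(−24/10)).

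| Course, carried BMI | R | 10% in each arm (R/10) | 5/15 active, 1/15 placebo (R/3) | 1/15 active, 5/15 placebo (R/15) |
|---|---|---|---|---|
| Plateau at week 8, monthly | 1.50 | 0.15 | 0.50 | 0.10 |
| Exponential, monthly | 2.43 | 0.24 | 0.81 | 0.16 |
| Linear, monthly | 3.50 | 0.35 | 1.17 | 0.23 |
| Plateau, height visits | 3.00 | 0.30 | 1.00 | 0.20 |
| Exponential, height visits | 3.69 | 0.37 | 1.23 | 0.25 |
| Linear, height visits | 4.50 | 0.45 | 1.50 | 0.30 |

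Section 14.4 does not say which BMI is carried. On each course the choice moves the result by 0.10 to 0.15 points at 10% attrition.

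*Reversal.* Let placebo lose 2% and active 8% by week 24, with half reached at the carried value. Losing 20% of placebo only gives 0 − 0.2 × 1 = −0.20, so the effect is overstated by 0.20.

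*Leavers who stop drug and regain fully.* The assigned-group difference is then 0.9 × 6 = 5.40. LOCF gives 5.55 to 5.85, overstating by 0.15 to 0.45. By-arm imputation from completers gives about 6.0, overstating by 0.60.

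**Simulation** (1,000 runs per case, 15 per arm, residual SD 5.89 built from an assumed random slope plus visit noise, robust SE, 20 imputations):

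- *3 of 30 missing at random.* LOCF shrinkage 0.16–0.34 (monthly) or 0.29–0.44 (height visits), RMSE 2.13–2.18, coverage 0.93–0.95. Imputation with an interim BMI matched to the leaver's last visit: bias within 0.02, RMSE 2.22–2.30, coverage 0.95–0.96.
- *5 of 15 active against 1 of 15 placebo.* LOCF shrinkage 0.77–1.21 (monthly) or 1.19–1.54 (height visits), coverage 0.90–0.93. Matched imputation: bias within 0.03, coverage 0.95–0.96.
- *Two largest active-arm losers removed at weeks 12–20.* LOCF shrinkage 0.34 (monthly) or 0.66 (height visits); matched imputation 0.00, relative to their having continued.

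**The case against.** For BMI, the case for leaving LOCF alone is a strong one. At the planned 10% attrition the bias is at most 0.45/2.15 = 0.21 of a standard error, coverage is near nominal, and LOCF has the lower RMSE. Even at 5 against 1, LOCF on monthly weights has the lower RMSE (2.20 against 2.31, and 2.33 against 2.35). It loses only if height-visit BMI is carried (2.37 and 2.47). That dropout split is an assumption. Section 2.2 reports a 6.1-point placebo-subtracted weight difference by day 56 in adolescents with obesity, which points to an early effect and the low end of the range. The near-zero bias of imputation is partly built in, because the simulated data suit a linear imputation model. All of this stands, and it makes the BMI gain modest.

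The plan also already has arm-stratified imputation, longitudinal analyses, the OGTT return visit and the offer of visits off drug. These help interpretation and reduce missingness, but the primary estimate remains the LOCF one.

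For the OGTT, section 14.4 nowhere states that baseline is carried forward. It follows from applying the primary rule similarly to a test with no interim measurement.

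A reader might go further and infer that unequal dropout always enlarges the BMI bias, that LOCF always errs on the cautious side, or that imputation is always better. The calculations support none of these. With 1 of 15 active and 5 of 15 placebo leaving, the shrinkage (0.10–0.30) is below that at equal 10% on every course. If placebo also loses weight, the sign can reverse. If leavers regain off drug, LOCF overstates the difference and imputation overstates it more.

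**Conclusion.** The point holds, and the OGTT outcomes are its main part. Under the primary rule a missing week-24 OGTT becomes zero change on three of five Aim 2 outcomes. That follows from the schedule and section 14.4, without any assumption about time course. The size and direction of the resulting bias do depend on assumptions: −10% at equal 10% missingness, and from −20% to +10% in the unequal examples.

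For BMI, assuming a true 6-point difference, a flat placebo arm and leavers who would have followed their arm's course, LOCF shrinks the estimate by about 0.15–0.45 points at equal 10% attrition. The figure is about 0.5–1.5 if 5 of 15 active and 1 of 15 placebo participants leave. It is smaller, and can reverse, when placebo loses more. The documents give no BMI course for this population, so these sizes are illustrative. They do not show that the primary analysis is invalid. The change is worth making because it needs no new data.

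**What to change.** In sections 14.3 and 14.4, before unblinding:

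1. **OGTT outcomes.** Make the baseline-adjusted analysis of observed week-24 values primary, or the already planned by-arm imputation from baseline, in place of baseline carried forward. Report the number missing and the reasons by arm, because with no interim OGTT neither option corrects for removal that depends on the outcome.
2. **BMI.** Make by-arm multiple imputation primary, using baseline BMI plus one interim BMI taken at the leaver's last attended visit (baseline alone if there is no interim weight). Completers should contribute their BMI at that same visit. Using their latest interim BMI instead left about half of the LOCF bias in the simulation (0.08–0.17). One added variable respects the plan's own limit. Keep LOCF as a sensitivity analysis, defined as last weight with last measured height.
3. **Assumption.** State that the imputation assumes leavers would have followed similar completers in their arm. Add a sensitivity analysis in which active leavers return toward placebo or baseline, since there imputation overstates the assigned-group difference by about 0.60 against 0.15–0.45 for LOCF.

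The cost is wording and some programming. At 10% attrition the BMI standard error rises by roughly 6–9% (2.22/2.09 = 1.06; 2.28/2.10 = 1.09), RMSE is slightly higher (2.21–2.30 against 2.11–2.18), and the imputation model rests on about 13 to 14 completers per arm.

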## 15.0 Health Information and Privacy Compliance

15.1 Select which of the following is applicable to your research:

- My research does not require access to individual health information and therefore assert HIPAA does not apply.
- I am requesting that all research participants sign a HIPCO approved HIPAA Disclosure Authorization to participate in the research (either the standalone form or the combined consent and HIPAA Authorization).
- I am requesting the IRB to approve a Waiver or an alteration of research participant authorization to participate in the research.

Appropriate Use for Research:

- An external IRB (e.g. Advarra) is reviewing and we are requesting use of the authorization language embedded in the template consent form in lieu of the U of M stand-alone HIPAA Authorization. Note: External IRB must be serving as the privacy board for this option.

15.2 Identify the source of Private Health Information you will be using for your research (Check all that apply)

- I will use the Informatics Consulting Services (ICS) available through CTSI (also referred to as the University's Information Exchange (IE) or data shelter) to pull records for me
- I will collect information directly from research participants.
- I will use University services to access and retrieve records from the Bone Marrow Transplant (BMPT) database, also known as the HSCT (Hematopoietic Stem Cell Transplant) database.
- I will pull records directly from EPIC.
- I will retrieve record directly from axiUm / MiPACS
- I will receive data from the Center for Medicare/Medicaid Services
- I will receive a limited data set from another institution
- Other.

- 15.3 Explain how you will ensure that only records of patients who have agreed to have their information used for research will be reviewed.

We will work with Fairview Research Administration to pull a pool of individuals who have agreed, in their electronic medical record, to learn about potential research studies. The data will be placed in the data shelter so that recruitment letters can be generated and sent to potential participants. Individuals who have indicated that they do not want to be contacted about research will not be approached.

- 15.4 Approximate number of records required for review: >10,000

- 15.5 Please describe how you will communicate with research participants during the course of this research. Check all applicable boxes

- This research involves record review only. There will be no communication with research participants.
- Communication with research participants will take place in the course of treatment, through MyChart, or other similar forms of communication used with patients receiving treatment.
- Communication with research participants will take place outside of treatment settings. If this box is selected, please describe the type of communication and how it will be received by participants.  
Subjects will receive telephone calls, virtual visits through the AmWell Platform, and emails regarding the study. The detail of telephone calls that this study requires is outlined in the consent form. Emails that contain PHI will be sent to the subject/parent in a secure, encrypted manner.

- 15.6 Explain how the research team has legitimate access to patients/potential participants:

This has been explained in other sections of the protocol.

- 15.7 Location(s) of storage, sharing and analysis of research data, including any links to research data (check all that apply).

- In the data shelter of the [Information Exchange \(IE\)](#)

Store       Analyze       Share

- In the Bone Marrow Transplant (BMT) database, also known as the HSCT (Hematopoietic Stem Cell Transplant) Database

Store       Analyze       Share

- In REDCap (recap.ahc.umn.edu)

Store       Analyze       Share

MEDICAL PROTOCOL PEDS-2021-29785

PROTOCOL TITLE: Phentermine/Topiramate in Adolescents with Type 2 Diabetes and Obesity

VERSION DATE: 10Dec2024

In Qualtrics (qualtrics.umn.edu)

Store       Analyze       Share

In OnCore (oncore.umn.edu) OnCore will serve as the EDC for the project

Store       Analyze       Share

In the University's Box Secure Storage (box.umn.edu)

Store       Analyze       Share

In an AHC-IS supported server. Provide folder path, location of server and IT Support Contact:

Store       Analyze       Share

In an AHC-IS supported desktop or laptop.

Provide UMN device numbers of all devices:

Store       Analyze       Share

Other. Describe:

Indicate if data will be collected, downloaded, accessed, shared or stored using a server, desktop, laptop, external drive or mobile device (including a tablet computer such as an iPad or a smartform (iPhone or Android devices) that you have not already identified in the preceding questions

I will use a server not previously listed to collect/download research data

I will use a desktop or laptop not previously listed

I will use an external hard drive or USB drive ("flash" or "thumb" drives) not previously listed

I will use a mobile device such as a tablet or smartphone not previously listed

*15.8* Consultants. Vendors. Third Parties. The CGM that is provided to the participant in the Discovery Clinic can collect and transmit data. The participant can choose, via the app, to share the data with the study team.

*15.9* Links to identifiable data:

Absolute confidentiality will be maintained. All data will be stored in locked offices and will not be released without consent of participants. Data to be used in scientific presentations or publications will not contain participant identifiers.

*15.10* Sharing of Data with Research Team Members.

Study team members will have access to the data shelter, REDCap, Box and to OnCore.

*15.11* Storage and Disposal of Paper Documents:

All data will be stored in locked offices and will not be released without consent of participants.

